2.2 Secondary Objectives

1. To determine the time to response (TTR), complete response rate (CRR), and duration of overall response (DoR) in subjects with advanced melanoma or metastatic TNBC when treated with Imprime PGG in combination with pembrolizumab
2. To measure the Progression-Free Survival (PFS) and PFS rate at 6 months and 1 year in subjects with advanced melanoma or metastatic TNBC when treated with Imprime PGG in combination with pembrolizumab
3. To measure overall survival (OS) and OS rate at 1 year in subjects with advanced melanoma or metastatic TNBC when treated with Imprime PGG in combination with pembrolizumab

4. To profile pharmacokinetic (PK) data in subjects with advanced melanoma or metastatic TNBC when treated with Imprime PGG in combination with pembrolizumab

2.3 Exploratory Objectives

1. Determine ORR and PFS based on irRECIST in subjects with advanced melanoma or metastatic TNBC when treated with Imprime PGG in combination with pembrolizumab
2. Correlate levels of baseline serum anti- β -glucan antibody (ABA) with objective response and treatment outcomes
3. Correlate changes in immune cell activation markers, such as CD86 expression in tumor biopsy samples and in peripheral blood immune cells with objective response and treatment outcome
4. In tumor biopsies, correlate changes in the tumor immune microenvironment including TILs (Tumor-infiltrating Lymphocytes) and tumor-infiltrating myeloid cells with objective response and treatment outcome
5. Correlate PD-L1 expression in tumor biopsy samples (in tumor cells and myeloid cells) with objective response and treatment outcome

3 END POINTS

3.1 Primary

The primary efficacy endpoint is ORR, which is defined as the proportion of subjects demonstrating complete response (CR) or partial response (PR) based on RECIST v1.1 criteria.

Safety endpoints include the incidence of adverse events, serious adverse events, laboratory safety tests (hematology, clinical chemistry, and urinalysis), and ECOG performance.

3.2 Secondary

Measurement of the secondary endpoints is based on RECIST v1.1 criteria.

- Time to response (TTR) is defined as time from first dose of study treatment (Study Day1) to first response (CR or PR)
- Complete response rate (CRR) is defined as the proportion of subjects demonstrating CR
- Duration of response (DoR) is defined as the time from the first documented evidence of CR or PR until time of documented disease progression (PD) or death due to any cause, whichever is first
 - For responders who are lost to follow-up or who discontinue study before PD or death, DoR will be censored at the date of last radiological assessment
- Progression-free survival (PFS) is defined as:
 - Time from Study Day 1 until PD or death due to any cause, whichever occurs first
 - For subjects who are lost to follow-up or who discontinue study before PD or death, PFS will be censored at the date of the last radiological assessment
- Overall survival (OS) is defined as:
 - Time from Study Day 1 until date of death due to any cause
 - For subjects who have not died or who are lost to follow-up or withdrew consent, OS will be censored at the date of last contact
- Pharmacokinetic profile

3.3 Exploratory

- ORR, as defined by irRECIST
- PFS, with date of PD as defined by irRECIST

The following exploratory analyses will be conducted to examine the relationship between biomarker data and endpoints if the data warrants:

- Analysis of ABA and endpoints
- Analysis of change in the immune cell activation markers and endpoints
- Analysis of change in the tumor immune microenvironment and endpoints

4 STUDY DESIGN

This is a Phase 2 study of Imprime PGG and pembrolizumab in subjects with advanced melanoma failing front-line treatment with checkpoint inhibitors or TNBC failing front-line chemotherapy for metastatic disease.

The study design is based on hypothesis testing of the ORR for pembrolizumab + Imprime PGG. For melanoma subjects, the null hypothesis is $ORR \leq 5\%$, versus the alternative hypothesis of $ORR \geq 23\%$; for the TNBC subjects, the null hypothesis is $ORR \leq 5\%$ ($ORR=5\%$ in KEYNOTE-086), and the alternative hypothesis is $ORR \geq 21\%$. Hypotheses testing will be conducted using a one-sided type I error of 0.05.

The study will incorporate Simon's optimal 2-stage design with sample size fixed at 12 subjects each in Stage 1 for advanced melanoma and for TNBC subjects. The safety criterion of ≤ 4 (or $\leq 33\%$) subjects with Grade 3/4 adverse events in Cycle 1 within either tumor type must be met in order to proceed to Stage 2 (Grade 3/4 infusion reactions which occur during Cycle 1 that either resolve or decrease to Grade 1/2 and recur in Cycle 2, will not be counted towards the total of ≥ 4). The starting dose is 4 mg/kg for Imprime PGG. In the event there are a total of > 4 (or $> 33\%$) of subjects with Grade 3/4 adverse events in Cycle 1, the dose of Imprime PGG will be reduced to 2 mg/kg, and Stage 1 will be repeated at a dose of 2 mg/kg with an additional cohort of $n=12$ subjects. For the dose that meets the safety criterion in Stage 1, at least 1 response in melanoma subjects and 1 response in TNBC subjects amongst the 12 subjects within each tumor type must be observed in order to proceed to Stage 2. Stage 2 will enroll an additional 17 subjects with melanoma, and 29 subjects with TNBC. For the dose that meets the Stage 1 safety criterion, success will be declared if at least 4 amongst the total of up to 29 subjects with melanoma, and 5 amongst the total of up to 41 subjects with TNBC achieve an objective response. The above design corresponds to a type I error 0.05 and power of 90% for both melanoma and TNBC.

The dosing schedule and the study assessments are presented in the schedule of assessment in the protocol.

All subjects will receive Imprime PGG and pembrolizumab. Imprime PGG will be administered IV at a dose of 4 mg/kg over a 2-hour infusion time period on Day 1, Day 8, and Day 15 of each 3-week cycle for subjects at stage 1. If Stage 1 proceeds without safety concerns necessitating a second cohort at 2 mg/kg, Imprime PGG will be administered to the Stage 2 subjects at a dose of 4 mg/kg IV over a 2-hour infusion time period on Day 1, Day 8, and Day 15 of each 3-week cycle. If enrollment into an additional cohort for 2 mg/kg in Stage 1 is required and dosing proceeds to Stage 2, Imprime PGG will be administered in Stage 2 at a dose of 2 mg/kg IV over a 2-hour infusion time period on Day 1, Day 8, and Day 15 of each 3-week cycle. The pembrolizumab fixed dose of 200 mg will be administered IV over 30 minutes on Day 1 of each 3-week treatment.

Subjects will be dosed until disease progression, death, 2 years of treatment or study completion, whichever occurs first. After treatment discontinuation, subjects will be monitored every 2 months for survival until death or study completion. Study completion is defined as the death of at least 70% of subjects or 3 years after the last subject's first dose, whichever occurs earlier.

Discontinuation of treatment may be considered for subjects who have attained a confirmed CR, who have been treated for at least 24 weeks, and who had at least 2 treatments with study medications beyond the date when the initial CR was declared. Subjects who then experience radiographic disease progression may be eligible for up to 1 year of additional treatment with Imprime PGG + pembrolizumab at the discretion of the Investigator if:

- No cancer treatment was administered since the last dose of pembrolizumab
- The subject meets the safety parameters listed in the Inclusion/Exclusion criteria
- The trial is open

Subjects will resume therapy at the same dose and schedule at the time of initial discontinuation. Response or progression in this resumed course of therapy will not count towards the ORR of the primary endpoint in this trial.

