### 2.1 Trial Design

The study will incorporate Simon's optimal 2-stage design with sample size fixed at 12 subjects each in Stage 1 for advanced melanoma and for Triple Negative Breast Cancer (TNBC) subjects. The safety criterion of  $\leq 4$  (or  $\leq 33\%$ ) subjects with Grade 3/4 adverse events in Cycle 1 within either tumor type must be met in order to proceed to Stage 2. The starting dose is 4 mg/kg for Imprime PGG. In the event there are a total of  $> 4$  (or  $> 33\%$ ) of subjects with Grade 3/4 adverse events in Cycle 1, the dose of Imprime PGG will be reduced to 2 mg/kg, and Stage 1 will be repeated at a dose of 2 mg/kg with an additional cohort of n=12 subjects. For the dose that meets the safety criterion in Stage 1, at least 1 response in melanoma subjects and 1 response in TNBC subjects amongst the 12 subjects within each tumor type must be observed in order to proceed to Stage 2.

Stage 2 will enroll an additional 17 subjects with melanoma, and 29 subjects with TNBC. For the dose that meets the Stage 1 safety criterion, success will be declared if at least 4 amongst the total of up to 29 subjects with melanoma, and 5 amongst the total of up to 41 subjects with TNBC achieve an objective response.

The study population will be those having failed front-line therapy, defined as any treatment regimen or regimens used specifically in the treatment of metastatic disease. Refer to [Section 5.1 on Entry Criteria](#) for the study-specific requirements.

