## 2.2 Trial Diagram

\* ≤ 4 subjects or 33% of Stage 1 subjects does not include infusion reactions (from either study drug) which were subsequently controlled and reduced in Cycle 1 via ameliorating actions, and which did not recur in Cycle 2

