## **3. Dose Reduction**

If a subject experiences an infusion reaction despite having been administered premedication and despite the infusion time being lengthened, the PI may re-challenge the subject at the next visit by dose reducing the Imprime PGG to 2 mg/kg.

All attempts should be made to ameliorate Grade 3/4 infusion reactions by the Investigator following the 3 recommendations provided above sequentially.

In Stage 1, any Grade 3/4 infusion reactions mitigated by these actions and either resolving or decreasing to Grade 1/2, if this mitigation occurs within Cycle 1 and the Grade 3/4 infusion reaction does not recur in Cycle 2, will not be counted towards the total of > 4 or 33% of Grade 3/4 adverse events which require halting the study in Stage 1 for each individual indication. Only Cycle 1 Grade 3/4 infusion reactions (or those which recur in Cycle 2) will be counted towards the total which would halt advancement to Stage 2.

- In the event there are a total of > 4 or 33% of Grade 3/4 adverse events in Stage 1 which were unable to be ameliorated by the sequential recommendations above, the dose of Imprime PGG will be reduced to 2 mg/kg.
- Stage 1 will be repeated with an additional cohort of n=12 subjects at the reduced dose of 2 mg/kg. Toxicity at the dose of 2 mg/kg will be assessed in this additional Stage 1 cohort in the same manner as was done for the initial dose of 4 mg/kg, with the identical sequential recommendations for any observed infusion reactions.
- Advancement to Stage 2 will be halted if there are > 4 or 33% of Grade 3/4 adverse reactions. Otherwise, subjects will proceed to Stage 2 with all subjects at the new, reduced dose of 2 mg/kg.

Note that continuation onto Stage 2 requires a demonstration of at least 1 or 2 objective responses in subjects with melanoma or TNBC, respectively, in addition to meeting the adverse event requirements detailed above, at either Imprime PGG dose of 4 mg/kg or 2 mg/kg. Please refer to the [Trial Diagram](#) in [Section 2.2](#) for a schema of the study flow from start to end.

In general, any Grade 4 non-infusion or non-hematological AE will lead to the withdrawal of the subject from treatment. A dosing delay of up to 3 weeks is allowed in case of Grade 3 non-hematological AEs to reduce toxicity to baseline or Grade 0-1. Dose levels will be adjusted individually for each study drug.

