Grades 3 or 4  Grade 3: Prolonged (ie, not rapidly responsive to symptomatic medication and/or brief interruption of infusion); recurrence of symptoms following initial improvement; hospitalization indicated for other clinical sequelae (eg, renal impairment, pulmonary infiltrates)  Grade 4: Life-threatening; pressor or ventilatory support indicated	
Stop Infusion.            Additional appropriate medical therapy may include but is not limited to:
 
 
Epinephrines**
 
IV fluids
 
Antihistamines
 
NSAIDS
 
Acetaminophen
 
Narcotics
 
Oxygen
 
Pressors
 
Corticosteroids
 
 
Increase monitoring of vital signs as medically indicated until the subject is deemed medically stable in the opinion of the Investigator.            Hospitalization may be indicated.            **In cases of anaphylaxis, epinephrine should be used immediately.  Subject is permanently discontinued from further study drug treatment.
	No subsequent dosing

Appropriate resuscitation equipment should be available at the bedside and a physician readily available during the period of drug administration.

For further information, refer to the Common Terminology Criteria for Adverse Events v4.03 (CTCAE) at <http://ctep.cancer.gov>

In Stage 1, any Grade 3/4 infusion reactions mitigated by these actions and either resolving or decreasing to Grade 1/2, if this mitigation occurs within Cycle 1 and the Grade 3/4 infusion reaction does not recur in Cycle 2, will not be counted towards the total of > 4 or 33% of Grade 3/4 adverse events which require halting the study in Stage 1 for each individual indication. Only Cycle 1 Grade 3/4 infusion reactions not controlled by the above measures (or those which recur in Cycle 2) will be counted towards the total which would halt advancement to Stage 2.

Dose will be managed individually for each study drug.

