### **9.1.3 Efficacy Analyses**

Efficacy analysis will be conducted separately for each tumor type. The primary efficacy endpoint is ORR, and the secondary efficacy endpoints include PFS, TTR, CRR, DoR and OS. The primary efficacy population will include all evaluable subjects who receive at least one dose of study treatment, have measurable disease at baseline per RECIST v1.1, and have at least one post-baseline scan or discontinue study treatment as a result of progressive disease, death, or a treatment-related adverse event before the first post-baseline scan.

Hypotheses testing of ORR will be conducted among evaluable subjects at the dose which meets the safety criterion in Stage 1. Among the 12 evaluable subjects in Stage 1, at least 1 objective response in melanoma subjects would be needed to proceed to Stage 2 for melanoma; and at least 1 objective response in TNBC subjects would be needed to proceed to Stage 2 for TNBC. If there are at least 4 objective responses among the total of 29 evaluable subjects with melanoma and/or at least 5 objective responses among the total of 41 evaluable subjects with TNBC, the null hypothesis will be rejected for melanoma and/or TNBC and the study will be declared a success.

The point estimate along with the exact 95% confidence interval will be computed for ORR and CRR. PFS and OS will be summarized descriptively and graphically using the Kaplan-Meier method. The Kaplan-Meier estimate for the median, first, and third quartiles will be determined along with 95% confidence intervals (CIs). The Brookmeyer-Crowley method will be used for the CI calculations. For the subset of subjects who have a CR or PR, TTR and DoR will be summarized similarly using the Kaplan-Meier method. The Kaplan-Meier

estimate of PFS rate at the landmark times of 6 months and 1 year, and the OS rates at the landmark time of 1 year will be calculated.

Exploratory analyses may be conducted using iRECIST.

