1 INTRODUCTION

This Statistical Analysis Plan (SAP) is to describe in detail the statistical analyses to be conducted for the protocol BT-CL-PGG-MEL/BCA-1621/MK3475 PN-545. This is a Phase 2 study of Imprime PGG and pembrolizumab in subjects with advanced melanoma failing front-line treatment with checkpoint inhibitors or triple negative breast cancer failing front-line chemotherapy for metastatic disease. All decisions regarding the interim, primary and final analyses will be made prior to the database freeze of the study data.

For further information on the study design, see Protocol BT-CL-PGG-MEL/BCA- 1621/MK3475 PN-545 version 2.0, dated 10August 2017.

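### SAP Section 4 reverses the recurrence condition for infusion reactions in the Stage 1 safety gate

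*SAP*

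**What the plan says.** Protocol Section 2.1 sets the gate. In each tumor type, at most 4 (33%) "subjects with Grade 3/4 adverse events in Cycle 1 within either tumor type must be met in order to proceed to Stage 2". Stage 1 has 12 subjects per tumor type. Above 4, the Imprime PGG dose falls to 2 mg/kg and Stage 1 is repeated with 12 more subjects.

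The protocol exempts some infusion reactions from this count and states the condition three times:

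- Section 2.2, diagram footnote: reactions controlled and reduced in Cycle 1 are left out, provided they are ones "and which did not recur in Cycle 2".
- Section 5.2.1.2.1, item 3 (Dose Reduction): a reaction mitigated within Cycle 1 that "does not recur in Cycle 2, will not be counted towards the total of > 4 or 33% of Grade 3/4 adverse events". It then adds: "Only Cycle 1 Grade 3/4 infusion reactions (or those which recur in Cycle 2) will be counted towards the total".
- Section 5.2.1.2.2, text after Table 2: the same exemption, followed by "Only Cycle 1 Grade 3/4 infusion reactions not controlled by the above measures (or those which recur in Cycle 2) will be counted".

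SAP Section 4 restates the gate and adds a parenthetical about Grade 3/4 events, saying that "infusion reactions which occur during Cycle 1 that either resolve or decrease to Grade 1/2 and recur in Cycle 2, will not be counted". It writes the limit there as ≥ 4. The sentence around the parenthetical passes the gate at ≤ 4, and a later sentence in the same paragraph fails it at > 4.

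SAP Section 5.1 reports, in the past tense, that an informal Stage 1 review assessed the safety criterion for each tumor type and confirmed the dose. It does not say how infusion reactions were counted.

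**The concern.** Read literally, the SAP exempts the reactions that the protocol counts (mitigated, then recurring) and gives no exemption to those that the protocol leaves out (mitigated, not recurring). That is clinically backwards, because a severe reaction that returns despite mitigation is the one a safety gate should register.

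The gate also fixes the dose for the primary analysis. Protocol Section 9.1.3 states: "Hypotheses testing of ORR will be conducted among evaluable subjects at the dose which meets the safety criterion in Stage 1". Anyone reconstructing the dose decision from the SAP would find only the reversed exemption there and could reach a different answer from the protocol's.

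**Working it through.** **1. The two rules side by side.** Put each Stage 1 subject in one class:

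| Class | Subject's Cycle 1 Grade 3/4 experience | Protocol | SAP Section 4, literal |
|---|---|---|---|
| A | Any other Grade 3/4 event, including an uncontrolled infusion reaction | counted | counted |
| B | Only a mitigated infusion reaction, recurs in Cycle 2 | counted | exempt |
| C | Only a mitigated infusion reaction, does not recur | exempt | counted |
| D | None | not counted | not counted |

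The protocol count is A + B and the literal SAP count is A + C. The gate fails when the count exceeds 4 of 12.

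**2. Drafting slip or changed rule?** The SAP gives no reason for a change, and its Introduction sends the reader to version 2.0 of the protocol: "For further information on the study design, see Protocol". Adding a negation before *recur* restores the protocol's recurrence condition. No other part of the SAP corrects the wording. A lost negation is an inference, but it is the simplest explanation.

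**3. Smallest case that changes the decision (no rates assumed).**

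- (A, B, C) = (4, 1, 0): protocol 4 + 1 = 5, fails; SAP 4 + 0 = 4, passes.
- (A, B, C) = (4, 0, 1): protocol 4 + 0 = 4, passes; SAP 4 + 1 = 5, fails.
- B = C = 0: both counts equal A, so the rules always agree.

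**4. How often the rules would disagree (illustration only).** The documents give no infusion-reaction rates for this combination, so the rates here are assumptions. Let a, b and c be the probabilities of classes A, B and C, with d = 1 − a − b − c. For A + B + C + D = 12,

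P(A, B, C, D) = 12! / (A! B! C! D!) × a^A b^B c^C d^D.

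Sum over outcomes in which exactly one of A + B and A + C exceeds 4. Each cell shows P(protocol fails, SAP passes) + P(protocol passes, SAP fails) = total.

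| b, c | a = 10% | a = 20% | a = 30% |
|---|---|---|---|
| 1%, 2% | 0.0019 + 0.0049 = 0.0068 | 0.0119 + 0.0275 = 0.0394 | 0.0222 + 0.0497 = 0.0719 |
| 2%, 4% | 0.0042 + 0.0127 = 0.0169 | 0.0219 + 0.0575 = 0.0794 | 0.0377 + 0.0946 = 0.1323 |
| 5%, 10% | 0.0136 + 0.0622 = 0.0758 | 0.0459 + 0.1646 = 0.2106 (parts rounded) | 0.0614 + 0.2066 = 0.2680 |

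The first term is the less protective direction: the SAP wording passes a dose that the protocol would fail.

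**5. Design figures.** The gate wording does not enter the response boundaries. Exact binomial sums for the stated designs (proceed with at least 1 response in 12; succeed with at least 4 of 29 or 5 of 41) give:

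- early termination under the null: 0.95^12 = 0.5404 in both cohorts (stated 0.54);
- melanoma: alpha 0.0500, power 0.902;
- TNBC: alpha 0.0452, power 0.906 (stated for both: 0.05 and 90%).

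These figures stand under either reading.

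**The case against.** The strongest reply concerns weight. The parenthetical sits in a recap of the design. The operative rule belongs to the protocol, which the SAP cites. The Stage 1 review was over when the SAP was written, and no analysis in SAP Sections 11 or 12 uses the gate count. All of that stands, and it keeps this from being a serious threat to the trial.

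The illustrative totals also need care. With c set at twice b, an arbitrary choice, about 69% to 82% of the disagreement is in the cautious direction (SAP fails, protocol passes). Table 2 also stops study treatment permanently after a Grade 3/4 pembrolizumab reaction, so recurrence would come essentially from Imprime PGG reactions, which bears on how large b could be. The table in step 4 shows sensitivity and says nothing about this trial's actual rates.

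It can also be said that a record of the past decision belongs in the Stage 1 review file or the study report, and that correcting the parenthetical is enough. The correction is indeed the essential part. But simply pointing to the protocol would not fully settle the count. Protocol Sections 2.1, 2.2 and 9.1.1 count subjects, whereas Sections 5.2.1.2.1 and 5.2.1.2.2 speak of a total of adverse events. The closing sentence on infusion reactions in 5.2.1.2.1 also lacks the qualifier about uncontrolled reactions that 5.2.1.2.2 has. One sentence in the SAP would remove the doubt.

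The ≥ 4 slip changes little by itself, since the same paragraph gives the limit correctly twice.

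**Conclusion.** The point holds. SAP Section 4 states the recurrence condition backwards against three consistent protocol statements, and nothing in the SAP corrects it. Because this is a decision rule for safety and dose, it should be fixed.

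Its reach is limited. The readings can differ only if at least one Stage 1 subject's sole Grade 3/4 event was a mitigated Cycle 1 infusion reaction; at the boundary, one such subject is enough to change the decision. Under the assumed rates above, disagreement runs from 0.7% to 26.8% of 12-subject cohorts, and the less protective part from 0.2% to 6.1%. There is no evidence that the reversed rule was applied. The consequence is confined to documenting and reproducing the dose and Stage 2 decision.

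**What to change.** In the SAP Section 4 parenthetical, insert *do not* before *recur* and change ≥ 4 to > 4.

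Add one sentence to SAP Section 5.1 stating the rule applied at the Stage 1 review. If it was the protocol rule, that sentence would say: subjects are counted; Grade 3/4 infusion reactions mitigated in Cycle 1 and not recurring in Cycle 2 are exempt; uncontrolled or recurring reactions are counted; the gate fails at more than 4 of 12.

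The cost is two wording corrections and one sentence, with no new data or analysis. Only if a different rule was used at the review would the 12 subjects per cohort need to be re-tabulated, with a statement of whether the dose or the Stage 2 decision changes.

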5 PLANNED ANALYSES

5.1 Interim Analyses

An informal interim analysis was conducted at the end of Stage 1 to assess the safety criterion for each tumor type and confirm the dose of Imprime PGG before continuing enrollment in Stage 2. Overall response rate based on RECIST 1.1 and adverse events including Grade 3/4 adverse events were considered for decision-making. Safety data will be summarized periodically throughout the study as part of ongoing safety review.

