- **System Organ Class (SOC) rows:** each subject is counted only once at the maximum grade at each SOC level although they may have several different preferred term events within the same SOC.
- **Any event row:** each subject with at least one AE will be counted only once at the maximum grade of all AEs he/she experiences.

All AEs and study treatment related AEs will be summarized by maximum toxicity grade, SOC and preferred term. Infusion reactions will be summarized similarly. In addition, AEs will be summarized by SOC and preferred term for the following time periods: 0-3, 3-6, 6-12 and >12 months.

A summary of non-serious AEs that occurred in strictly 5% of subjects or above will be provided (no rounding for the percentage will be used in terms of 5% threshold, e.g., event with 4.9% incidence rate will not be included in this table).

The listing of all AEs and Grade III/IV will be provided. Separate listing of infusion reaction, adverse events of new cancer (that is not a condition of the study) and adverse event associated with pembrolizumab overdose as determined by clinical team review will also be provided.

Listing of AEs (if any) may be provided for the screen failure or non-treated subjects in the Screening population and the subjects in the ABA Pre-screening population.

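### SAP 4 reverses the infusion-reaction exemption in the Stage 1 safety count: it leaves out reactions that recur in Cycle 2, where the protocol leaves out only those that do not

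*SAP*

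**What the plan says.** SAP 4 fixes Stage 1 at 12 subjects per tumor type. A count of 4 or fewer passes. A count above 4 lowers Imprime PGG to 2 mg/kg and repeats Stage 1. A parenthesis inside that rule, about Grade 3/4 reactions, says that "infusion reactions which occur during Cycle 1 that either resolve or decrease to Grade 1/2 and recur in Cycle 2, will not be counted", and gives the total as ≥ 4.

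The protocol states the exemption in three places:

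- Section 5.2.1.2.1 (Dose Reduction) says a mitigated Grade 3/4 infusion reaction, "if this mitigation occurs within Cycle 1 and the Grade 3/4 infusion reaction does not recur in Cycle 2, will not be counted".
- Section 5.2.1.2.2, below Table 2, gives the same exemption and adds: "Only Cycle 1 Grade 3/4 infusion reactions not controlled by the above measures (or those which recur in Cycle 2) will be counted".
- The footnote to the diagram in Section 2.2 leaves out reactions controlled in Cycle 1 "and which did not recur in Cycle 2".

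Four other places bear on the point:

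- SAP 1 ties the SAP to protocol version 2.0: "For further information on the study design, see Protocol".
- SAP 5.1 reports: "An informal interim analysis was conducted at the end of Stage 1 to assess the safety criterion for each tumor type".
- Protocol 9.1.3 confines the response-rate (ORR) test to the dose that passed the criterion.
- Protocol 9.1.6 plans an adverse event summary at the interim, including events of Grade 3 or higher.

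**The concern.** The exemption exists so that a severe reaction brought under control, and staying under control, does not count against the dose. As written, SAP 4 forgives the reaction that came back despite mitigation. It gives no exemption to the one that did not come back. That defeats the purpose of the rule.

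The criterion decides the Imprime PGG dose and, through Protocol 9.1.3, which subjects enter the ORR test. SAP 4 is the only place in the SAP that states the exemption; SAP 5.1 mentions the safety criterion without defining it. Anyone describing or rebuilding the Stage 1 count from the SAP alone would have only the reversed rule to work from.

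**Working it through.** **Wording side by side.**

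| Mitigated Grade 3/4 infusion reaction in Cycle 1 | Protocol 2.2, 5.2.1.2.1, 5.2.1.2.2 | SAP 4, read literally |
|---|---|---|
| Does not recur in Cycle 2 | Left out | Counted (no exemption covers it) |
| Recurs in Cycle 2 | Counted | Left out |

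The SAP sentence is complete and grammatical, so lost text does not explain it. SAP 1 announces no departure from the protocol. The ≥ 4 in the parenthesis also conflicts with its own paragraph, which passes 4 and fails above 4. Two slips in one parenthesis suggest that a negation was dropped.

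**Effect on the count.** Inputs: 12 subjects per tumor type, pass if the count is at most 4 (SAP 4; Protocol 2.1 and 9.1.1). Count subjects, and define:

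- o = subjects counted under both rules;
- m = subjects with no other countable event whose mitigated reaction does not recur;
- r = subjects with no other countable event whose mitigated reaction recurs in Cycle 2.

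Protocol count = o + r. Literal SAP count = o + m. Difference = (o + r) − (o + m) = r − m, so the counts agree when r = m.

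| o | m | r | Protocol count | SAP count |
|---|---|---|---|---|
| 3 | 0 | 2 | 3 + 2 = 5, fail | 3 + 0 = 3, pass |
| 3 | 2 | 0 | 3 + 0 = 3, pass | 3 + 2 = 5, fail |
| 4 | 0 | 1 | 4 + 1 = 5, fail | 4 + 0 = 4, pass |
| 4 | 1 | 0 | 4 + 0 = 4, pass | 4 + 1 = 5, fail |

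With only one kind of mitigated reaction present, the verdicts part once that kind reaches 5 − o subjects: 1 when o = 4, 2 when o = 3, 3 when o = 2, 4 when o = 1, 5 when o = 0. With o of 5 or more, both rules fail. The error can run either way. Table 2 of the protocol ends dosing after a Grade 3/4 pembrolizumab reaction, so r would come from Imprime PGG reactions.

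**Whether a planned output would show the right count.** SAP 12.2 says "AEs will be summarized by SOC and preferred term for the following time periods: 0-3, 3-6, 6-12 and >12 months". With the SAP's month of 30.4375 days, the first period is 3 × 30.4375 = 91.3 days, or 91.3 / 21 = 4.3 cycles, so it does not isolate Cycle 1. The interim summary in Protocol 9.1.6 covers Stage 1, but nothing says that it applies the exemption. SAP 12.2 also plans a "Separate listing of infusion reaction, adverse events of new cancer", among others. The adjusted count can be rebuilt from these listings, but no planned output displays it.

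**ORR design.** The exemption enters neither the response thresholds (1 of 12, then 4 of 29 or 5 of 41) nor the response probabilities behind them. The stated alpha, power and early-termination figures therefore do not change.

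**The case against.** The strongest reply is that this is editorial. The sentence is a recap in a design section. No planned SAP table, listing or test computes the count, the SAP points to the protocol for the design, and the protocol gives the rule correctly in three places. The Stage 1 review is over and no consequence has been shown. All of these facts stand, and they limit the point to reporting. They do not make it clerical: the sentence states the criterion that selects the dose for the primary test, and followed literally it can give the opposite verdict.

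Three narrower objections also stand:

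- The numerical cases sit at the cut by choice. The documents give no values for o, m or r, so the cases show that a split is possible and say nothing of how likely it is.
- It would be wrong to say that no Stage 1 safety summary is planned, because Protocol 9.1.6 plans one. What is missing is the exemption-adjusted count.
- Rebuilding that count is more than copying a figure. Someone must judge for each subject whether the reaction was mitigated within Cycle 1 and whether it recurred.

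A reader might infer that the reversed rule set the Imprime PGG dose, or let a dose into Stage 2 that should have failed. The documents do not support that. SAP 5.1 puts the review in the past tense and does not say how infusion reactions were counted. The protocol carried the correct rule.

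**Conclusion.** The contradiction is definite. SAP 4 reverses the protocol's exemption, and no other SAP text corrects it. A dropped negation is by far the likeliest cause.

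The size is bounded. The two counts differ by r − m subjects. One subject can flip the verdict when o = 4, and more are needed below that. This assumes that the criterion counts subjects, as Protocol 2.1, Protocol 9.1.1 and SAP 4 say; Protocol 5.2.1.2.1 and 5.2.1.2.2 refer more loosely to a total of events. It also takes the SAP sentence at its word.

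Because the Stage 1 review has been done under a rule that the documents do not identify, the remaining risk is that the study report describes or re-derives the criterion by the reversed rule. The SAP should be corrected, but the point does not call the ORR design into question.

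**What to change.** 1. In the SAP 4 parenthesis, insert the missing negation so that the reactions left out are those that do not recur in Cycle 2, and change ≥ 4 to > 4.
2. In the study report, give for each tumor type the Stage 1 subject count under the protocol rule, and state which rule was used for the dose decision.

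The first is a one-sentence edit. The second needs a subject-level check of Stage 1 infusion reactions, using the adverse event and infusion-reaction listings already planned in SAP 12.2, with clinical input on mitigation and recurrence. Neither requires more subjects, procedures or data.
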